Specific Aim 2. Subjects will complete six experimental sessions at the University of Colorado Locomotion Laboratory; each session on a separate day and requiring approximately two hours of time. During each experimental session, subjects will run and sprint over a range of speeds, from 3 m/s up to top speed on a force measuring treadmill while we measure their ground reaction forces, socket pressures, and socket pistoning. Subjects will run with three different brands (Ossur, Ottobock, and Freedom Innovations) of sprint-running RSPs with at least three different stiffnesses at one height and three different heights at one stiffness of each brand, a total of five or more different conditions per brand. Individual trials at each speed will be approximately 15-30 seconds long with at least 2 minutes rest between trials.

A safety harness attached to the ceiling above the treadmill and handrails beside the treadmill will be used during all running/sprinting trials to ensure subjects' safety. Each running trial will consist of at least 10 strides. To begin each trial, subjects will lower themselves from the handrails on to the moving treadmill belt. For each prosthetic stiffness and height condition, subjects will start a series of trials at 3 m/s, each subsequent trial will be incremented by 1 m/s until subjects approach their top speed, and then smaller speed increments will be employed until subjects reach their top speed. *Top speed* will be determined when subjects put forth maximal effort but cannot maintain their position on the treadmill for ten strides (Weyand, Sternlight, Bellizzi, & Wright, 2000). Subjects will be given as much time between trials as needed to recover fully (at least 2 minutes). At least seven trials will be performed by each subject for each prosthetic condition (e.g. 3, 4, 5, 6,

7, 7.3, 7.5 m/s) and a maximum of three series of trials will be performed each day. Our results will allow us to determine the optimal RSP mechanical stiffness (k_{opt}) and height (h_{opt}) for each person. The optimal sprint-running (SR) RSP will be the prosthesis that maximizes top speed.

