Day SR0: Subjects will be asked to give informed written consent and then will be fit and aligned by a certified prosthetist with three different sprint-running RSP brands, one from each company. We will measure each subject's height, weight, and limb segment lengths. Then, we will select an RSP stiffness category based on the subject's weight and manufacturer's recommendation. An appropriate RSP height for each subject will be chosen according to conventional practice. Our prosthetist will ensure that the prosthetic fit and alignment are adequate. Then, subjects will have time to accommodate to treadmill running and sprinting with each sprintrunning RSP over a range of speeds.

Day SR1: We will first vary the sprint-running RSP stiffness (k) while keeping height (h) at the recommended level. Subjects will use an RSP with the manufacturer's recommended stiffness category based on their weight, an RSP that is one category softer (k-) and an RSP that is one category stiffer (k+) than the manufacturer's recommended stiffness. We will measure ground reaction forces, top speed, socket pressures, and socket pistoning while subjects run and sprint over a range of speeds from 3 m/s up to their top speed. If the data warrant it, we may add an additional stiffness category to further fine tune the optimal stiffness. The optimal stiffness (k_{opt}) sprint-running RSP will be the RSP that maximizes top speed. This RSP stiffness will be used for Day SR2.

Day SR2: We will keep RSP stiffness constant (k_{opt}) and vary the sprint-running RSP height (h). Subjects will have used an RSP with an optimal stiffness (k_{opt}) at the recommended height (h_R) on day Day SR1. On Day SR2, they will also use and RSP with an optimal stiffness (k_{opt}) that is 2 cm shorter (h-), and 2 cm taller (h+). We will measure ground reaction forces, top speed, socket pressures, and socket pistoning while they run across a range of speeds from 3 m/s up to their top speed. If the data warrant it, we may further fine tune RSP height in 1 cm increments. We will analyze the results of SR2 to identify the optimal height (h_{opt}) for each subject for one brand of a sprint-running RSP

Days SR3 and SR5: We will repeat the trials of Day SR1 and vary stiffness (k) for a different sprint-running RSP brand. We will analyze the results of Days SR3 and SR5 to identify the optimal RSP stiffness (k_{opt}) to be used for Days SR4 and SR6.

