Socket Pressure. We will measure the pressure at the residual limb-socket interface using a thin wireless pressure sensor (Tekscan Wireless F-socket bipedal system, South Boston, MA) that attaches to the skin of the residual limb via adhesive spray. These data will be sampled at 160 Hz and synched with the ground reaction force data. The pressure sensor will provide information about peak pressure magnitude and location. Based on previous studies that have measured socket pressure during walking (Abu Osman, Spence, Solomonidis, Paul, & Weir, 2010; Ali et al., 2012; Dumbleton et al., 2009), we define excessive socket pressure as a peak socket pressure that exceeds 100 kPa. We have been unable to find any scientific reports of socket pressures during running. To further understand how subjects sense socket pressure, we will ask each subject to rate their perceived pressure on a scale of 0-10 following each trial, where 0 equals no pressure, 5 is perceived as "acceptable for a 10km run", and 10 equals intolerable pressure.

Socket Pistoning. We will measure the axial movement of the residual limb within the socket dynamically using reflective markers and a motion capture system (Vicon Motion Systems, Centennial, CO). Prior to data collection, a cluster of reflective markers will be placed on the socket and on the thigh of the residual limb to measure movement within the socket (pistoning) during running. These data will be sampled at 200 Hz and synched with the ground reaction force data. Based on previous studies that have measured socket pistoning during walking (Eshraghi, Abu Osman, Gholizadeh, Karimi, & Ali, 2012; Gholizadeh et al., 2011), we define excessive socket pistoning as a displacement of the residual limb relative to the socket that exceeds 8 cm. To further understand how subjects sense socket pistoning, we will ask each subject to rate their perceived pistoning on a scale of 0-8 following each trial, where 0 equals no pistoning, 5 is perceived as an "acceptable amount of pistoning" and 8 equals excessive pistoning.

D. Description, Risks and Justification of Procedures and Data Collection Tools:

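### The sprint optimum rests on one effort-dependent top-speed series per stiffness, with no concealment of the recommended category, no encouragement script and no fixed final step, so expectation may shift it by an unknown amount

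*Combined protocol and SAP*

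**What the plan says.** Section IV.C, Specific Aim 2, defines top speed by two conditions together: subjects "put forth maximal effort but cannot maintain their position on the treadmill for ten strides". Each series climbs from 3 m/s in 1 m/s steps. Near the limit, "smaller speed increments will be employed until subjects reach their top speed"; the size of these increments is not given. The illustrative ladder ends "7, 7.3, 7.5 m/s) and a maximum of three series of trials will be performed each day".

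On Day SR0 the study team sets the reference blade: "we will select an RSP stiffness category based on the subject's weight and manufacturer's recommendation". Subjects then accommodate to sprinting with each brand. On Day SR1 that blade is compared with "an RSP that is one category softer (k-) and an RSP that is one category stiffer (k+) than the manufacturer's recommended stiffness", and the decision rule is "The optimal stiffness (k_{opt}) sprint-running RSP will be the RSP that maximizes top speed". The chosen stiffness is carried to Day SR2, where only the 2 cm shorter and 2 cm taller settings are new. The recommended-height result is the one already obtained on Day SR1. Days SR3 to SR6 repeat this for the other two brands.

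Under Measurements and Analysis subjects also give ratings: "we will ask each subject to rate their perceived pressure on a scale of 0-10 following each trial" and "we will ask each subject to rate their perceived pistoning on a scale of 0-8 following each trial".

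No section mentions masking the subject or the treadmill operator, covering category markings, scripting encouragement, or who judges that effort was maximal. Section IV.E (Potential Scientific Problems) discusses fatigue and added conditions, but not expectation.

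**The concern.** The only criterion for k_opt is a performance limit that the subject's effort helps to set. Staff also have discretion at three points: accepting the effort as maximal, encouraging the subject, and choosing the next increment. Subjects have at least one year on sprint prostheses (section IV.B) and may hold views about stiffness. The investigators state one of their own in section III, where a stiffer blade is thought likely to be needed for top speed. If the subject or operator knows which blade is which, effort or encouragement may differ between settings.

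A shift in one series goes further than that day. It can change k_opt, and so the stiffness used on the height day. It can also raise or lower the Day SR1 speed against which the two other heights are judged. From there it reaches the comparison of top speed across conditions (section IV.C), the recommendation given to the subject (section IV.D) and the planned prescription algorithms (section IV.G).

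**Working it through.** The plan gives no figure for expectation effects, trial-to-trial variation in top speed, or true differences between stiffnesses, so there is nothing to reproduce. The check has three parts.

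**1. Series per stiffness.** Day SR1 has 3 settings (recommended, softer, stiffer), and the daily maximum is 3 series. 3 / 3 = 1 series per stiffness. Extra days are allowed if fatigue appears or conditions are added, but no replicate series is planned, so an effort difference in one series would not be exposed by a second.

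**2. Size of one step.** The example ladder ends at 7, 7.3 and 7.5 m/s.
- 7.5 − 7.3 = 0.2 m/s; 0.2 / 7.5 = 2.7%.
- 7.3 − 7.0 = 0.3 m/s; 0.3 / 7.3 = 4.1%.

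One more or one fewer completed step therefore moves recorded top speed by about 3-4%. The ladder is only an example, so the real steps may differ.

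**3. Sensitivity of choosing the fastest of three.** Assumptions, none taken from the documents: three equally good stiffnesses; independent normal variation with standard deviation σ of 0.1 to 0.3 m/s; and a shift b in favour of one blade. With one series each, the chance that the favoured blade is chosen is

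P = ∫ φ(x − b/σ) Φ(x)² dx.

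A simulation of 400,000 draws gave the values below for continuous speeds and, in brackets, for speeds recorded in 0.2 m/s steps with ties broken at random. The integral agrees with the continuous values to within 0.1 percentage point.

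| σ (m/s) | b = 0 | b = 0.1 | b = 0.2 |
|---|---|---|---|
| 0.1 | 33% (33%) | 63% (55%) | 87% (76%) |
| 0.2 | 33% (33%) | 48% (47%) | 64% (61%) |
| 0.3 | 33% (33%) | 43% (43%) | 53% (53%) |

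Equally good blades are the most sensitive case. Suppose instead that the favoured blade is truly 0.1 m/s slower than both others. Putting b = −0.1 in the integral gives 11% (σ = 0.1), 21% (0.2) and 25% (0.3) without bias. Adding a shift of 0.2 m/s leaves a net advantage of 0.2 − 0.1 = 0.1 m/s, so the b = 0.1 column applies: 63%, 48% and 43%. With larger true gaps, a one-step shift matters less.

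These figures show how the decision rule responds to a shift of about one step. They do not estimate how large any shift in this trial would be.

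**The case against.** Five points can be made for the plan.

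- **The end point is partly objective.** Losing position within ten strides at a set belt speed is an observable event, and the protocol cites a published method for it. A reader might infer that staff judgement alone ends a series, or that an operator can credit an extra step. The text does not support that, because the subject must physically hold the speed. What stands is that failure counts only if effort was maximal, that effort helps decide when position is lost, and that encouragement and the next increment are left open.
- **The direction is not shown.** A reader might infer a systematic bias that persists however many subjects are studied. Section III leans towards stiffer blades for sprinting, but section IV.E expects some optima to be softer and some stiffer than recommended. Expectations may differ between subjects. A shared one would not average out over 15 subjects, but the documents do not establish that there is one.
- **The ratings do not choose the blade.** The pressure and pistoning ratings are open to expectation too. They do not enter the k_opt rule and are absent from the list of analysed data in section IV.C, so this is a secondary matter.
- **Masking would be incomplete.** Subjects may feel stiffness, and accommodation on Day SR0 follows selection of the recommended category, so they may already know that blade. Height and brand stay open. This stands, and covering labels only from Day SR1 would be too late.
- **Staffing and added conditions.** The protocol does not say who runs the treadmill, and an extra stiffness may be added if the data call for it, so someone must link speeds to categories. The fix has to allow for both.

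**Conclusion.** The gap is real but limited. The sole sprint criterion depends on effort, normally comes from one series per stiffness, ends on an unfixed increment, and is collected without concealment of category or standard encouragement. Expectation may therefore shift k_opt and the Day SR1 comparator used on Day SR2. One step in the example ladder is 0.2-0.3 m/s (2.7-4.1%), which could change the choice when stiffnesses are close. For three equally good blades and an assumed σ of 0.1-0.3 m/s, a 0.2 m/s shift raises selection of the favoured blade from 33% to between 53% and 87%.

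The documents give neither the size nor the direction of any such bias, so they do not support concluding that expectation will decide the optimum. The case for acting is that the safeguard is cheap. The unfixed increment and unscripted encouragement are the firmest part, because they can be corrected whether or not masking works.

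**What to change.** 1. **Standardise the test for every setting, including height and brand.** Pre-set one final speed increment. State one criterion for a failed trial (for example, position not held for ten strides, with the same repeat-attempt rule throughout). Use one fixed encouragement script.
2. **Code the stiffness settings from Day SR0 to the end of each brand's sessions.** Cover the category markings, use neutral codes, and do not tell the subject which category is recommended. Where existing staff allow the fitter and the treadmill operator to be different people, keep the operator unaware as well. The fitter holds the key and links results to categories if an extra stiffness is considered.
3. **State the limits.** Say that masking is partial because subjects may feel stiffness, and that height and brand remain open.

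The cost is covered labels, a code sheet, a short script and one added rule, with no extra visits and no requirement for extra staff. The downside is minor logistics and incomplete masking. If the sponsor finds coding impracticable, item 1 still applies and the protocol should record the limitation.

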Cover Page

Title: What is the optimal stiffness and height of a running-specific leg prosthesis?

NCT #: N/A

Date of Document: 9/30/2014

PROTOCOL #: 13-2315

COMIRB Protocol

COLORADO MULTIPLE INSTITUTIONAL REVIEW BOARD [name] [contact] [contact]

Project Title: What is the optimal stiffness and height of a running-specific leg prosthesis?

Principal Investigator: [name].

I. Hypotheses and Specific Aims:

Our *primary objective* is to optimize prescription of **running-specific prostheses (RSP)** for Soldiers and Veterans with transtibial amputations by systematically varying RSP stiffness and height during running and sprinting.

Specific Aim 1: We aim to quantify the biomechanics (how someone moves), metabolic demands (how much energy is required to move), socket pressures (pressure within a prosthetic socket), and socket pistoning (axial displacement of the residual limb relative to the socket) of subjects with transtibial amputations using three brands (Ossur, Ottobock, and Freedom Innovations) of distance-running RSPs of different stiffness and height.

Hypothesis 1: The optimal stiffness and height distance-running RSP for each subject will minimize asymmetry and metabolic demand, without excessive socket pressure or socket pistoning.

Specific Aim 2: We aim to quantify the biomechanics, performance, socket pressures and socket pistoning of subjects with transtibial amputations using three brands (Ossur, Ottobock, and Freedom Innovations) of sprint-running RSPs of different stiffness and height.

Hypothesis 2: The optimal stiffness and height sprint-running RSP for each subject will minimize asymmetry and maximize top speed, without excessive socket pressure or socket pistoning.

II. Background and Significance:

Currently, there are no science-based objective methods for prescribing **running specific leg prostheses (RSPs)**. Thus, existing clinical practices waste time, money, and resources and do not necessarily optimize RSP prescription for Soldiers with leg amputations. Our **overall goal** is to develop a science-based method for optimal prescription of RSPs so that Soldiers and Veterans with leg amputations can regain the greatest possible level of functional ability and return to an active lifestyle and/or active duty.

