We do not yet know how prosthetic stiffness affects overall leg stiffness while running and sprinting. During running in non-amputees, the overall biomechanics of the body are wellcharacterized and predicted by a spring-mass system that represents the body's mass as a point mass and the legs as mass-less linear springs (Blickhan, 1989; Brughelli & Cronin, 2008; Farley & Ferris, 1998; Farley, Glasheen, & Mcmahon, 1993; He, Kram, & McMahon, 1991; McMahon & Cheng, 1990). During the first half of the stance phase of running, the kinetic and gravitational potential energies of the body are stored as elastic energy in the leg. During the second half of the stance phase, this elastic energy is returned to the body. At slow to moderate speeds (2-6 m/s), previous studies have shown that leg stiffness is independent of speed in non-amputees (Farley et al., 1993; He et al., 1991; McGowan et al., 2012; Morin, Dalleau, Kyrolainen, Jeannin, & Belli, 2005). Thus, an optimal distance-running RSP stiffness for an individual with a unilateral amputation would be expected to result in an overall affected leg + prosthesis stiffness that is equal to the overall unaffected leg stiffness. This optimal stiffness would likely minimize biomechanical asymmetry and metabolic demand. At speeds greater than 6 m/s, non-amputee runners progressively increase their leg stiffness with speed (McGowan et al., 2012). Thus, it is probable that a stiffer prosthesis is required to maximize top speed (McMahon & Greene, 1979). Given that the biological leg spring compresses by only 2.0-2.5 cm during the stance phase of running (Farley & Gonzalez, 1996; McGowan et al., 2012), changing the height of an RSP by just one cm could also profoundly affect the dynamics of the spring mass model.

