Day DR1: We will first vary the distance-running RSP stiffness (k) while keeping height (h) at the traditionally recommended level. Subjects will use an RSP with the manufacturer's recommended stiffness category based on their weight, an RSP that is one category softer (k-) and an RSP that is one category stiffer (k+) than the manufacturer's recommended stiffness. We will measure ground reaction forces, metabolic demand, socket pressures, and socket pistoning while subjects run at the speed required for their age/sex 50th percentile PFT (Physical Fitness Test) 2 mile run and at 3 m/s, a total of six trials. If the data warrant it, we may add an additional stiffness category to further fine tune the optimal stiffness. The optimal stiffness (k_{opt}) distance-running RSP will be the RSP that minimizes metabolic cost. This RSP stiffness will be used for Day DR2.

 $\underline{\text{Day DR2:}}$ We will keep RSP stiffness constant (k_{opt}) and vary the distance-running RSP height (h). Subjects will have used an RSP with an optimal stiffness (k_{opt}) at the recommended height (h_R) on day Day DR1. On Day DR2, they will also use and RSP with an optimal stiffness (k_{opt}) that is 2 cm shorter (h-), and 2 cm taller (h+). We will measure ground reaction forces, metabolic demand, socket pressures, and socket pistoning while they run at their PTF speed and at 3 m/s; a total of four trials. If the data warrant it, we may further fine tune RSP height in 1 cm increments. We will analyze the results of DR2 to identify the optimal height (h_{opt}) for each subject for one brand of a distance-running RSP.

Days DR3 and DR5: We will repeat the trials of Day DR1 and vary stiffness (k) for a different distance-running RSP brand. We will analyze the results of Days DR3 and DR5 to identify the optimal RSP stiffness (k_{opt}) to be used for Days DR4 and DR6.

Days DR4 and DR6: We will repeat the trials of Day DR2 and vary height (h) for a different distance-running RSP brand. We will analyze the results of Days DR4 and DR6 to identify the optimal height (hoot) for each subject using the respective brand of a distance-running RSP.

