In Specific Aim 1, we propose to have subjects complete a total of six running trials per day and each trial will last 5 minutes. In Specific Aim 2, we propose to have subjects complete three sets of running and sprinting trials from 3 m/s up to top speed and each trial will last approximately 30 seconds. The proposed experimental trials may be too difficult, long, and/or exhausting. However, we have previously conducted up to eight running economy trials without detecting any effects of fatigue (Grabowski & Kram, 2008; Teunissen, Grabowski, & Kram, 2007). Moreover, our previous studies of Paralympic athletes with transtibial amputations suggest that subjects can complete three sets of running and sprinting trials from 3 m/s up to top speed without showing effects of fatigue (Grabowski et al., 2010). Thus, we believe that our proposed experimental protocol will be adequate; however if we do see signs of fatigue, we may need to spread out the protocol over more days.

We expect to find that for some subjects the optimal stiffness is either softer or stiffer than the manufacturer's recommended stiffness or that the optimal height is taller or shorter that the traditionally recommended height. Therefore, it may be necessary to add conditions to our protocol so that we can establish the true minimum metabolic cost or maximum speed. On Days 2, 4, and 6, we would be able to test an additional stiffness and height condition without exceeding the recommended number of trials per session. If additional trials are necessary, we may need to add an additional day to our protocol.

F. Data Analysis Plan:

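### The top-speed part of Hypothesis 2 and the metabolic-cost part of Hypothesis 1 (for stiffness) are true by definition; the parts that can fail have no stated test in the selected prosthesis, and the comparison with the recommended setting is not a hypothesis

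*Combined protocol and SAP*

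**What the plan says.** **Hypotheses (section I).** Hypothesis 1 says the optimal distance-running "RSP for each subject will minimize asymmetry and metabolic demand, without excessive socket pressure or socket pistoning". Hypothesis 2 says the optimal sprint-running "RSP for each subject will minimize asymmetry and maximize top speed, without excessive socket pressure or socket pistoning".

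**Selection rules (section IV.C).**
- Sprint, overall (Specific Aim 2): "The optimal sprint-running (SR) RSP will be the prosthesis that maximizes top speed".
- Sprint stiffness k_opt (Day SR1): "sprint-running RSP will be the RSP that maximizes top speed".
- Distance stiffness k_opt (Day DR1): "distance-running RSP will be the RSP that minimizes metabolic cost". Each stiffness is run at two speeds, and no rule says which speed decides or how the two are combined.
- Distance height (Day DR2): "We will analyze the results of DR2 to identify the optimal height", with no criterion. Section IV.E implies one, since conditions may be added "so that we can establish the true minimum metabolic cost or maximum speed".

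**Tests (section IV.C).** Each variable is compared across conditions by repeated-measures ANOVA with a follow-up procedure, at p < 0.05. Leg symmetry is an outcome in section IV.A but is not named in the section IV.C list of analysed data. The socket limits are 100 kPa and 8 cm (Measurements and Analysis).

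**Use of the result.** Subjects are to receive a recommendation of their optimal prosthesis (section IV.D, Potential Benefits), and prescription algorithms are to be developed from the data (section IV.G).

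**The concern.** If the optimum is defined as the setting with the best measured cost or speed, a hypothesis that it has the best cost or speed is confirmed whatever the data show. A prescriber needs to know something else: does choosing a setting this way beat following the manufacturer's recommendation? No hypothesis states that, and no planned comparison sets the selected stiffness against the recommended one on runs that played no part in selecting it. A benefit read off the selecting runs would include the luck of the best of several noisy measurements, and could be carried into the individual recommendations and the algorithms.

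**Working it through.** The plan gives no power, effect size or SD, so there is no figure of its own to reproduce.

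**1. Hypothesis components against selection rules.**

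| Component | In the selection rule? | Can it fail? |
|---|---|---|
| H2 top speed | Yes | No |
| H1 metabolic cost, stiffness | Yes (Day DR1) | No, at the speed used to select |
| H1 metabolic cost, height | Implied only (IV.E) | Not if that criterion is used |
| Asymmetry (H1, H2) | No | Yes |
| Socket pressure and pistoning (H1, H2) | No | Yes |

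**2. How the components behave with no true effect.** Assumptions: independent normal run errors, one brand, one speed, three stiffnesses and then two further heights; 400,000 simulated subjects. The selected setting has the best measured cost in 100% of subjects. It also has the least asymmetry in 33% (three stiffnesses) or 20% (five conditions) if errors in cost and asymmetry are uncorrelated, rising to 70% and 61% at an assumed correlation of 0.8. In Aim 1, the stiffness that is cheapest at one speed is also cheapest at the other in 33%.

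**3. Apparent gain over recommended, from the selecting runs, with no true effect.** For three independent standard normal errors, E[min] = −3/(2√π) = −0.846. The recommended run has expectation 0, so the expected gain is 0 − (−0.846) = 0.85 run-error SD. It reaches 1.16 SD after the height stage. A one-sample t test of the stiffness-stage gain (n = 15, three brands) gives p < 0.05 in essentially every simulated trial, and in 98% with one brand.

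**4. The ANOVA.** Over softer, recommended and stiffer, labelled by category, selection does not enter: rejection with no effect is about 5% (n = 15). The height comparison differs. Day DR2 has four trials, which is 2 new heights × 2 speeds, so the recommended-height run at k_opt is carried over from Day DR1. If that already-selected run is compared with the two fresh heights, a one-brand null simulation (n = 15) rejects in about 72%.

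**5. Why the stiffness ANOVA does not answer the individual question.** Suppose half the subjects are best one category softer and half one category stiffer, losing 1 SD per category away from their optimum. The group means are (0 + 2)/2 = 1 at softer, 1 at recommended and (2 + 0)/2 = 1 at stiffer. They are flat, although every subject would gain 1 SD by changing.

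**6. Leave-one-brand-out.** For each subject, choose the offset (softer, same, stiffer) on two brands, measure its gain over recommended in the third, average the three splits, and apply a one-sample t test over 15 subjects.

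| Scenario | Optima split two ways | Optima split three ways |
|---|---|---|
| Shared across brands, 1 SD per category | gain 0.82, power about 85% | gain 0.46, power about 35% |
| Shared across brands, 0.5 SD per category | power about 15 to 17% | power about 4% |
| Brand-specific, 1 SD per category | power about 2% | power about 0.1% |

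With no effect, the mean gain is 0.00 and a favourable false claim occurs in about 1.5%.

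**The case against.** - **The hypotheses are not empty.** A reader might infer that nothing could contradict them. The documents do not support that: asymmetry and the socket limits are in no selection rule. A fair reading is that the setting best for cost or speed will also be the most symmetric and within limits. Section III adds a mechanistic prediction, that matched leg stiffness is best: "This optimal stiffness would likely minimize biomechanical asymmetry and metabolic demand". This stands, and it confines the circularity to the cost and speed components.
- **The plan never proposes the biased comparison.** A reader might infer that the planned analysis yields a false benefit in nearly every trial. It does not; those figures belong to a test of k_opt against recommended that is not prespecified. The ANOVA over stiffness categories is valid and does compare softer and stiffer with recommended. This also stands, but only for group means, and section IV.E expects optima to differ between subjects.
- **Some runs at k_opt did not select it.** True: the shorter and taller runs on the height days are new. They differ from recommended in height as well, so they do not isolate the gain from stiffness.
- **Leave-one-brand-out can miss real benefit.** The plan selects k_opt afresh for each brand, and power vanishes if optima are brand-specific. This stands and governs how the test must be labelled.
- **The study is meant to develop guidelines.** That lowers the weight of hypothesis wording, but guidelines rest on the same selected optima.

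**Conclusion.** The concern holds for the top-speed component of Hypothesis 2 and the metabolic-cost component of Hypothesis 1, explicitly for stiffness and by implication for height. The asymmetry and socket components can be contradicted, but no test of them in the selected prosthesis is stated. The gain over the recommended setting is not a hypothesis; taken from the selecting runs it is biased upward by about 0.85 run-error SD with no true effect. That size assumes three independent normal runs of equal variance, and the SD unit is an assumption. The planned stiffness ANOVA is sound as a group-level test. The height comparison is not, if it uses the carried-over k_opt run. This should be changed, though it does not invalidate the study.

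**What to change.** 1. Reword Hypotheses 1 and 2 so that they can fail: the setting selected on metabolic cost (Aim 1) or top speed (Aim 2) beats the recommended setting on runs not used to select it, and also has the least asymmetry and stays within the stated socket limits. Name the symmetry measure and, for Aim 1, the speed or combination of speeds that decides. Read asymmetry from held-out runs too, since errors correlated with cost would favour agreement.
2. Keep the ANOVA over softer, recommended and stiffer as the group-level test.
3. Add the leave-one-brand-out gain over recommended, with a one-sample t test over subjects, labelled as a test of a stiffness offset shared across brands. Do not report the gain of k_opt over recommended from the selecting runs as evidence of benefit.

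Selection of k_opt for the height day can proceed as planned. Optionally, repeating k_opt at the recommended height on the height day would remove the carry-over problem. It makes 4 + 2 = 6 trials in Aim 1 and 2 + 1 = 3 series in Aim 2, both within the plan's daily numbers, but uses room that section IV.E keeps for added conditions.

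**Cost:** new wording for two hypotheses and one analysis of runs already planned. The estimated benefit will be smaller. Power is modest unless optima are shared across brands and the effect is large, so a null result would not rule out brand-specific benefit. The added test covers stiffness only, not height.
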